4.2.3. Patient withdrawal criteria

The patient will be removed from the study when any of the following circumstances are met:

- Patients who have not had both plasma infusions.
- Unacceptable toxicity.
- Withdrawal of the IC.
- Completion of the study.
- Exitus.

Patients will be informed that they can leave the study at any time without affecting their medical care in the future. The reason and date of departure of the study will be recorded in the patient's medical history.

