4.2.2 Exclusion criteria

For the receiver:

A. Recipients hospitalized in COVID-19 plant:

1. Patients with a previous history of allergic reaction to any type of transfusion of blood products.
2. Breastfeeding women or women with pregnancy potential and positive pregnancy test.
3. Patients who have been treated with plasma in the 21 days prior to the screening/baseline visit.
4. Patients who, in the opinion of the researcher, possess any condition that makes the recruitment of the same incompatible.
5. Patients who are at the time of the study, participating in a clinical trial.
6. Patients who have not performed all the procedures in the study.

For the donor:

1. Plasmapheresis in the last 7 days.
2. Blood donation in the last 7 days.
3. Donation of more than 25 L of plasma in the previous 12 months.
4. With the intention of reducing the risk of transfusion-related acute lung injury (LPART/TRALI), only male donors never transfused and women with no history of abortions will be selected.

5. Patients who are at the time of the study, participating in a clinical trial.

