4.2.4. Research treatment

1. Description of the processing

Plasma of convalescent patients with antibodies against Coronavirus SARS-CoV-2 compatible with receptor. **This plasma will reinforce the standard treatment that will be prescribed in these patients, following the guide of "Clinical management of COVID-19 patients", where the usual medications in these patients and their management are detailed.**

2. Labelling and storage of research processing

The plasma will be labelled and stored as set forth in the apheresis section of the receiver.

3. Administration of study treatment

600 ml of plasma from ex-convalescent patients' compatible ABO group shall be administered peripherally or centrally intravenously every 24 hours on days 1 and 2 from treatment assignment, divided into two doses of 300 ml each. **The 600 ml of plasma will ideally come from a single donor patient, failing that plasma from different donors may be administered if they are from the same compatible ABO group, recording the final titration of the two doses administered.**

5. Accounting of the study treatment

The principal investigator of the study will be responsible for the registration of the transfused plasma units using the accounting form. Patient code, identification code of the administered plasma unit, expiration date and date of administration must be recorded. This form must be kept together with the documentation of the study in case of audit or inspection.

6. Description of control treatment

The control treatment will consist of what is indicated in the COVID-19 management protocols according to usual clinical practice and in accordance with the clinical management protocol of the patient hospitalized for COVID-19. The full duration of the treatment will be determined by what is specified in the protocols. All medication will be provided by the pharmacy service of the Son Llàtzer University Hospital (or where appropriate the pharmacy services corresponding to each centre participating in the study), following usual clinical practice.

7. Criteria for discontinuation of study treatment

The following situations will lead to permanent discontinuation of study treatment:

- Exitus.
- Life-threatening toxicity to the patient, including infusion-related reactions.

8. Concomitant medication

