4.2.9. Adverse events

4.2.9.1. Monitoring and recording of adverse events.

An adverse event (AA) is any harmful, unintended, or unfavourable medical event that occurs or worsens in a patient over the course of a study. It may be a new concurrent disease, the worsening of a concomitant disease, an injury, or any concomitant deterioration of the patient's state of health, including its analytical results regardless of its cause. Any worsening (i.e., any adverse and clinically significant variation in the frequency or intensity of an ailment that was present prior to study treatment) should be considered an AA. The diagnosis or syndrome is recorded in the Data Collection Notebook (CRD).

The investigator must record all non-serious and severe AAs related to the study treatment that occur from the signing of the informed consent up to 30 days after the last dose of the investigational treatment. Severe AA (AAG) that occurs after the signing of the informed consent but before initiating treatment should also be recorded.

The assessment of the AA will include the following aspects:

- Gravity: An AAG is all AA that https://correu.ssib.es/owa/-_msocom_1 :

1. Deathrolls.
2. Threaten life (an AA that, in the opinion of the investigator, carries an immediate risk of death).
3. Hospitalization or prolongation of hospitalization is necessary (hospitalization is defined as a hospital admission, regardless of the length of stay). Scheduled hospitalization, for socio-sanitary reasons or, for this study, that derived from COVID-19, will not be considered an AAG.
4. Persistent or significant disability or disability (substantial impairment of the patient's ability to perform normal activities).
5. Give rise to a congenital anomaly or birth defect.
6. It is an important medical event.

-Severity: The severity/intensity of adverse events (AA) is classified based on the patient's symptoms according to the current version of the toxicity criteria common for adverse events (CTCAE, Version 5.0);

https://ctep.cancer.gov/protocoldevelopment/electronic_applications/docs/CTCAE_v5_Quick_Reference_5x7.pdf

- Causal relationship: The relationship will be defined as **suspicious** in a situation where there is a reasonable possibility that the administration of the investigational medicinal product caused the adverse event. When there is a remote or low probability that the event is related to the study drug then the relationship will be defined as non-suspicious.

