4.3.2. Duration of the study

In version 1.0 of the study, the estimated study duration period was 3 months from the date of compliance with the Clinical Research Ethics Committee (in Spain CEIm) Research Ethics Committee (CEIm) and Spanish Agency for Medicines and Health Products (in Spain AEMPS). In this version 2.0 the study period is extended to recruit a sufficient n to be able to estimate the effectiveness of the treatment or failing that until the competent authorities so determine. The follow-up period for patients will be 21 days from the start date of the study and if necessary, it will be extended as long as necessary, in order to ensure patient safety.

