		2	Past infection
		3	Immunized
		4	Negative
CMV Serology		0	Negative
		1	Positive
Syphilis Serology		0	Negative
		1	Positive
INMHEMATOLOGIC STUDY			
ABO Blood Group		0	A
		1	B
		2	AB
		3	O
Rh		0	Present
		1	Absent
Irregular Blood Group antibodies		0	Negative
		1	Positive
DIAGNOSTIC/MICROBIOLOGICAL PROCEDURES			
Quantitative titration of SARS-COV2 antibodies (IgG/IgM)		UA/mL	Number
RT-PCR SARS-COV-2		0	Negative
		1	Positive

Time to RT-PCR negativization	Days		Number
CLINICAL CRITERIA			
Pleural effusion		0	Negative
		1	Positive
PSI score		1	Valuation not required
		2	<=70
		3	71 - 90
		4	91 - 130
		5	>130
WHO Progression Scale		0	Uninfected; no viral RNA detection.
		1	Asymptomatic; viral RNA detection
		2	Symptomatic. Independent
		3	Symptomatic. Need for assistance
		4	Hospitalized. Oxygen-free
		5	Hospitalized. Oxygen with mask or nasal tips
		6	Hospitalized. Oxygen by non-invasive ventilation (NIV) or high flow.
		7	Intubation or mechanical ventilation. PO2/FIO2>= 150; or SpO2/FO2> 200
		8	Mechanical ventilation (pO2/FIO2< 150, or SpO2/FIO2< 200), or vasopressor (norepinephrine >0.3 microg/Kg/min)
		9	Mechanical ventilation (pO2/FIO2< 150, or SpO2/FIO2< 200), or vasopressor (norepinephrine >0.3 microg/Kg/min) o dialysis o ECMO
% of patients requiring ICU admission			Number
15-day mortality rate			Number
Mortality rate at 30 days			Number
Days of hospitalization			Number
SECURITY CRITERIA			
Emerging adverse effects (ASD) \geq GIII		0	No
		1	Yes
Type TEAE SPECIFY			Name
Cumulative rate/incidence of ASD \geq GIII in experimental branch			Number

Cumulative rate/incidence of emerging adverse events (ASD) any grade in experimental branch			Number
Hospital discharge date			Date
Exitus		0	Yes
		1	No

Table 1. Variables that will be included in the database of the study.

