5. DATA ANALYSIS: STATISTICS

A descriptive analysis of all variables will be performed. With the categorical variables, the global percentages and frequencies will be estimated. Normality tests and graphs will be used to determine if the quantitative variables follow a normal distribution. Normal distribution variables shall be expressed as mean \pm standard deviation and those without normal distribution shall be expressed as median and interquartile range. To describe the significance and associations between variables after the intervention, parametric and non-parametric tests will be used as appropriate (the student's t test of paired samples or the Wilcoxon test for quantitative variables and the ANOVA test for paired samples or Friedman test for qualitative variables). The correlations will be examined by the correlation of Spearman or Pearson ranges and a multivariate analysis will be performed to assess the effect of other factors such as the confusion/interaction effect, as well as to assess the possible construction of predictive models. A p-value $< 0,05$ shall be considered an indicator of a significant difference. SPSS v.23 software will be used for data analysis.

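### Removing patients who miss a plasma infusion, with no analysis set defined, leaves the efficacy comparison open to post-assignment selection bias of unknown size and direction

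*Combined protocol and SAP*

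**What the plan says.** Section 4.2.3 opens its list of withdrawal criteria with "The patient will be removed from the study when any of the following circumstances are met". The list names "Patients who have not had both plasma infusions", unacceptable toxicity, withdrawal of consent, completion of the study and death. Stopping treatment has a separate list in section 4.2.4, item 7, which names death and "Life-threatening toxicity to the patient, including infusion-related reactions".

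In section 4.2.2, exclusion 6 for ward recipients reads "Patients who have not performed all the procedures in the study".

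Section 5 is the only statistics section. Its statement on testing is "To describe the significance and associations between variables after the intervention, parametric and non-parametric tests will be used as appropriate". It names no analysis population, no rule for patients with no infusion or only one, and no handling of missing outcomes. Section 4.1 adds an analysis stratified by type of treatment, again without a population.

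On follow-up, section 4.3.2 says "The follow-up period for patients will be 21 days from the start date of the study", with extension where safety requires it. Table 1 in section 4.3.3 lists 15-day mortality and "Mortality rate at 30 days". Section 4.2.9.1 records adverse events related to study treatment "up to 30 days after the last dose of the investigational treatment".

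**The concern.** Infusions are given on days 1 and 2 (sections 4.1 and 4.2.4), so whether a patient has had both is known only after assignment. Controls receive no plasma. Read literally, the criterion removes every control; read sensibly, it acts in the plasma arm alone. Death and severe toxicity are among the documents' own routes to a missed second infusion, and both are bound up with the outcome. If the analysis keeps only plasma patients with both infusions, one arm is selected on an early post-assignment event and the other is not, so random assignment no longer protects the comparison.

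Three consequences follow:

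- The efficacy estimate can be shifted in either direction.
- Patients removed alive may have no vital status at day 30, and this cannot be repaired at the analysis stage.
- Table 1 asks for adverse-event rates in the experimental branch, but no denominator is defined, so the rates depend on who is left after removal.

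Ward exclusion 6 points the same way, because completing the study procedures cannot be known at enrolment. It is not arm-specific.

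**Working it through.** The documents give no sample size, event rate, dropout rate or early-death rate, so there is no planned figure to reproduce. What follows is an illustration, and its clinical inputs and total sample sizes are assumptions.

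**Inputs**

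- *From the documents:* infusions on days 1 and 2 (section 4.1); control to treated ratio 1:2 (section 4.1, which also describes equal-probability assignment); threshold 0.05 (section 5).
- *Assumed:* no true effect; 15-day mortality *m* = 10%, 20% or 30% in both arms; share of plasma patients dying before infusion 2, *x* = 1%, 3% or 5%; share of survivors missing infusion 2, *s*; total N = 100 or 300.

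**Step 1: observed plasma mortality when only patients with both infusions are kept**

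Observed = (m − x) / [(m − x) + (1 − m)(1 − s)]

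With m = 0.20 and s = 0:

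- x = 0.01: 0.19/0.99 = 19.2%
- x = 0.03: 0.17/0.97 = 17.5%
- x = 0.05: 0.15/0.95 = 15.8%

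The control arm stays at 20%, so the apparent benefit is 0.8, 2.5 and 4.2 points with no real effect.

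**Step 2: false results favouring plasma**

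The rates come from 400,000 simulated trials per cell, with control N/3, plasma 2N/3, and a pooled two-proportion z-test with z < −1.96. The nominal rate is about 2.5%; with x = 0 the simulated rate is 2.6% to 2.9%. At m = 0.20 and s = 0:

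| x | N = 100 | N = 300 |
|---|---|---|
| 1% | 3.5% | 3.9% |
| 3% | 5.4% | 8.0% |
| 5% | 8.4% | 15.2% |

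Over the whole grid the lowest rates are 3.2% (N = 100) and 3.4% (N = 300), at m = 0.30, x = 0.01. The highest are 15.3% and 33.6%, at m = 0.10, x = 0.05. Those top values require half of all deaths to fall before infusion 2 (0.05/0.10).

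**Step 3: direction**

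The bias is zero when s = x/m. With m = 0.20 and x = 0.03, that is s = 0.15.

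- s = 0.05: 0.17/(0.17 + 0.76) = 18.3%, bias −1.7 points (favours plasma)
- s = 0.15: 0.17/(0.17 + 0.68) = 20.0%, bias 0
- s = 0.30: 0.17/(0.17 + 0.56) = 23.3%, bias +3.3 points (against plasma)

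**Step 4: the same trial analysed as assigned**

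With all assigned patients kept, expected plasma mortality equals m whatever x and s are, and the bias under no effect is zero.

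**The case against.** The withdrawal list also contains completion and death. If removal meant exclusion from the analysis, every completer and every death in both arms would go, which is absurd. It may therefore mean only that participation ends, in which case the list is silent on analysis. This is a fair reading, and it is why the conclusion is limited to the comparison being open to bias. It does not settle the matter: no passage says the data are kept, and in an open-label trial the choice could be made after the results are seen.

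Deaths are database variables, so patients who died before infusion 2 can be put back in the denominator. The false-result rates above all take s = 0 and so describe exactly that correctable loss. This stands, but only if the analysis plan requires the correction. It does not help patients removed alive, for whom 21-day follow-up does not assure a day-30 status.

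The gap between infusions is about 24 hours, ward patients must have SOFA ≤ 6, and one donation is meant to supply both bags, so few may miss infusion 2 and a 30% share of survivors doing so is unlikely. At 1% early deaths the inflation is small. ICU patients with SOFA > 6 are also enrolled, however, and the documents give no estimate.

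Finally, this is a phase I pilot whose main objective ends in immunological efficacy, and mortality is not named as primary. Mortality is used here only to give the problem a scale. The selection affects any outcome compared between arms.

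**Conclusion.** The concern holds and should be fixed before analysis. The removal rule is conditional on treatment received after assignment, works in one arm only, and is not overridden by any analysis set or by a commitment to continue follow-up. Size and direction cannot be determined from the documents. Under the assumptions shown, with early deaths as the only loss, false results favouring plasma range from about 3% to 15% with 100 patients and 3% to 34% with 300, against about 2.5% nominal. The upper ends are extreme cases. The routes the documents name (death and toxicity before infusion 2) would tend to favour plasma, while survivors missing infusion 2 push the other way.

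**What to change.** 1. In section 5, define the main analysis set as all randomised patients, analysed in the assigned arm. Patients placed in control without randomisation because plasma stock ran out are not part of this set.
2. Make patients who received both infusions a sensitivity set, and everyone who received any plasma the plasma-arm safety set.
3. In section 4.2.3, state that missing an infusion, or toxicity, does not end outcome follow-up, and obtain vital status at day 15 and day 30. Count death as an outcome, not as a reason for removal from the analysis.
4. Delete ward exclusion 6 in section 4.2.2, or restate it as a condition that can be judged at enrolment.
5. As a coding point, add a death level to the WHO scale in Table 1, which stops at 9; death is at present coded only under ECOG and Exitus.
6. The toxicity wording in sections 4.2.3 and 4.2.4 differs and the sponsor must reconcile it. No stopping rule is proposed here.

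The cost is amendment and analysis wording, plus one vital-status check at day 30 by telephone or records, beyond the 21-day schedule. The downside is that the main estimate includes incompletely treated patients and may be slightly diluted; the both-infusions sensitivity set shows how far the result depends on this.

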4.2.4. Research treatment

1. Description of the processing

Plasma of convalescent patients with antibodies against Coronavirus SARS-CoV-2 compatible with receptor. **This plasma will reinforce the standard treatment that will be prescribed in these patients, following the guide of "Clinical management of COVID-19 patients", where the usual medications in these patients and their management are detailed.**

2. Labelling and storage of research processing

The plasma will be labelled and stored as set forth in the apheresis section of the receiver.

3. Administration of study treatment

600 ml of plasma from ex-convalescent patients' compatible ABO group shall be administered peripherally or centrally intravenously every 24 hours on days 1 and 2 from treatment assignment, divided into two doses of 300 ml each. **The 600 ml of plasma will ideally come from a single donor patient, failing that plasma from different donors may be administered if they are from the same compatible ABO group, recording the final titration of the two doses administered.**

5. Accounting of the study treatment

The principal investigator of the study will be responsible for the registration of the transfused plasma units using the accounting form. Patient code, identification code of the administered plasma unit, expiration date and date of administration must be recorded. This form must be kept together with the documentation of the study in case of audit or inspection.

6. Description of control treatment

The control treatment will consist of what is indicated in the COVID-19 management protocols according to usual clinical practice and in accordance with the clinical management protocol of the patient hospitalized for COVID-19. The full duration of the treatment will be determined by what is specified in the protocols. All medication will be provided by the pharmacy service of the Son Llàtzer University Hospital (or where appropriate the pharmacy services corresponding to each centre participating in the study), following usual clinical practice.

7. Criteria for discontinuation of study treatment

The following situations will lead to permanent discontinuation of study treatment:

- Exitus.
- Life-threatening toxicity to the patient, including infusion-related reactions.

8. Concomitant medication

Any concomitant medication is allowed for the treatment of concomitant pathologies presented by the patient as well as the symptoms associated with COVID-19, including standard anticoagulant treatment that is prescribed under normal conditions (if applicable).

9. Prohibited medication

There is no contraindicated medication in the study treatment.

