4.2.9.2. Reporting of adverse events

The sponsor or designated person is responsible for reporting the AAG to the Research Ethics Committee and for providing it with all relevant initial and follow-up information about the event. The researcher must keep a copy of all AAG information in his or her file, including correspondence with the sponsor and the Research Ethics Committee.

The researcher must keep copies of all AAG information in a file, including correspondence with the sponsor.

The sponsor or designated person shall notify the relevant Authorities of all relevant and unexpected information on AAG suspected of being related to the study medication, causing death or threatening life, as soon as possible and in any case within a maximum period of seven days of becoming aware of them. Relevant follow-up information on these cases will be notified subsequently, within an additional eight days.

Any other serious and unexpected event suspected to be related to the study medication, as soon as possible, but within a maximum period of fifteen days after the investigator becomes aware of them. The researcher should keep a copy of all relevant security information in his or her file.

-Contact details of the promoter (coincides with the fact that he will be the person in charge of communicating the AA):

[name]

Son Llàtzer University Hospital, Internal Medicine Service

[contact]

[contact], [name]

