Since from the beginning of the pandemic to the present day no effective treatment against SARS-CoV-2 infection has been found; whereas it has also been shown that the disease has a high probability of progressing rapidly into more severe forms, causing death even in vulnerable groups; whereas the forecast for late summer-start autumn 2020 is being met; whereas there are no prevalence/incidence numbers or any other type of definitive numerical data that allows canonical sample size calculations to be made; whereas the few studies that have been published on the treatment of hyperimmune plasma infection have shown a positive trend towards decreasing symptoms and severity; and that finally we continue to find ourselves in a health emergency situation; so for all these reasons this study is transformed into a multicentre study, at the request of the participating centres. Therefore, it is required, in order to estimate with maximum efficiency, the effect of this therapy, the maximum number of donors and the maximum number of possible recipients. Each case is explained below:

-For donors: it is required to collect the plasma sample from the maximum number of people who meet the requirements to be donors. This aims to create an anti-SARS-CoV-2 hyperimmune plasma bank, so that not only for this study, but for serious situations in which all the possibilities available so far have been exhausted, this therapy can be used as an alternative. The difficulty of finding suitable donors, who not only meet the requirements to be donors, but also have a sufficient antibody titration, forces us to make accurate donor lists in order to have this type of sample in sufficient quantity. Being a multicentre study, more doses of plasma will be needed to be able to supply all the centres. Considering that the ratio is 1 donor or 1 donation for each recipient.

-For recipients: as it is unknown how many patients can progress in the coming weeks/months with COVID-19, it is required to propose participation in the study to all patients who are diagnosed with COVID-19 and admitted to the plant or ICU for COVID-19 of all participating centres. In this way, the maximum number of patients can be collected, in order to cover a sufficient sample size in the two branches of comparison of the study (control and treatment). As patients are admitted, they will be proposed to participate by explanation and with the HIP, and if they sign the IC, they will become part of it.

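### No trial-level pause is tied to the grade III or higher event rate in the plasma branch, and the number of plasma recipients has no stated maximum

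*Combined protocol and SAP*

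**What the plan says.** Section 2 states that convalescent plasma is not yet shown to be safe and effective, and section 4.1 describes a phase I pilot.

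- **Exposure.** Section 4.2.10 gives no sample size and asks for "the maximum number of donors and the maximum number of possible recipients". Section 4.3.2 extends the study to "recruit a sufficient n to be able to estimate the effectiveness of the treatment or failing that until the competent authorities so determine".
- **Toxicity rules.** Section 4.2.4 lists two reasons to stop study treatment permanently: death, and "Life-threatening toxicity to the patient, including infusion-related reactions". Section 4.2.3 removes a patient for unacceptable toxicity, which it does not define. The same list includes "Patients who have not had both plasma infusions".
- **Safety variable.** Under its safety criteria, Table 1 in section 4.3.3 has "Cumulative rate/incidence of ASD" at grade III or higher in the experimental branch. It is entered as a number, with no limit or consequence.
- **Recording and reporting.** Section 4.2.9.1: "The investigator must record all non-serious and severe AAs related to the study treatment", from consent to 30 days after the last dose. Section 4.2.9.2: "The sponsor or designated person is responsible for reporting the AAG to the Research Ethics Committee". Serious, unexpected, suspected events also go to the authorities, within seven days if fatal or life-threatening and fifteen otherwise.
- **Infusion monitoring.** Section 4.2.8 records adverse effects of each infusion through haemovigilance for 24 hours, with transfusion supervised by a haematology specialist.
- **Analysis.** Table 2 in section 4.3.4 schedules data analysis while recruitment is running. Section 5 describes no interim or safety analysis.

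**The concern.** If plasma caused more severe related reactions than the investigators would accept, a team following this plan to the letter would not be obliged to pause. A pause would depend on the sponsor, the ethics committee or the authorities noticing a pattern in single-event reports and choosing to act. With no maximum number of recipients, exposure has no planned end either. Running out of plasma sends patients to control (section 4.1), but that limits exposure by supply, not by harm.

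The rate in Table 1 also has an undefined denominator. A patient whose first infusion is stopped by a reaction does not receive the second and so meets a withdrawal criterion. The plan does not say whether that patient stays in the rate.

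**Working it through.** **1. Does any provision act on the trial as a whole because of a rate?**

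| Provision | Acts on | Rate named | Required action on plasma assignment |
|---|---|---|---|
| 4.2.3 withdrawal | one patient | none | none |
| 4.2.4 discontinuation | one patient | none | none |
| 4.2.8 haemovigilance to 24 h | one infusion | none | none (recording) |
| 4.2.9.2 reporting | one serious event | none | none (notification) |
| 4.3.2 authorities' decision | the trial | none | discretionary |
| 4.3.3 Table 1 grade III or higher rate | plasma branch | none | none |
| 4.3.4 analysis during recruitment | not specified | none | none |

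No row has both a rate and a required action. The figure of fewer than 100 inpatients in section 4.2.10 is background to version 1.0 and not a cap.

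**2. Who sees a non-serious grade III reaction?** Section 4.2.9.1 has the investigator record it, and section 4.2.8 has infusion effects recorded for 24 hours. The reporting duties in section 4.2.9.2 cover serious events only. No section sends a non-serious one promptly to the sponsor.

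**3. Can the right denominator be built?** Yes. The accounting form in section 4.2.4 states: "Patient code, identification code of the administered plasma unit, expiration date and date of administration must be recorded". That identifies everyone who received plasma, whether or not a second dose followed.

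**4. What would a rule do?** The plan has no boundary or tolerable rate to reproduce, so every input here is assumed: limit 5%, up to 60 plasma patients, a check every 10, prior Beta(0.05, 0.95), and a pause at the smallest x of at least 2 for which P(rate > 0.05 | x of n) exceeds 0.93. The posterior is Beta(0.05 + x, 0.95 + n − x).

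- n = 10: x = 2 gives 0.921 and x = 3 gives 0.990, so the boundary is 3.
- n = 30: x = 3 gives 0.821 and x = 4 gives 0.943, so the boundary is 4.
- n = 60: x = 6 gives 0.925 and x = 7 gives 0.972, so the boundary is 7.

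The full boundary is 3/10, 4/20, 4/30, 5/40, 6/50, 7/60.

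Let f_k(y) be the probability of y events at check k with no earlier pause. Then f_k(y) = Σ f_{k−1}(x) · C(10, y−x) p^(y−x) (1−p)^(10−y+x), summed over x below the previous boundary. The pause probability at check k is the sum of f_k(y) over y at or above that check's boundary.

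At p = 0.10 the first check gives 1 − 0.349 − 0.387 − 0.194 = 0.070. The six checks give 0.070 + 0.083 + 0.207 + 0.078 + 0.053 + 0.040 = 0.531. The first three alone give 0.360.

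| True rate | Pause by 60 | Pause by 30 | Mean treated, of 60 |
|---|---|---|---|
| 2% | 0.004 | 0.003 | 59.9 |
| 5% | 0.091 | 0.065 | 57.4 |
| 10% | 0.531 | 0.360 | 44.9 |
| 15% | 0.876 | 0.683 | 31.4 |
| 20% | 0.981 | 0.880 | 22.8 |

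Two sensitivities:

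- **Late reports.** If half the events became known only 10 patients later (assumed; 200,000 simulated trials), the pause probabilities at 5%, 10% and 20% would be 0.06, 0.43 and 0.96.
- **A different limit.** With a 10% limit, prior Beta(0.10, 0.90) and cutoff 0.95, the boundary is 4, 5, 7, 8, 10, 11. It pauses with probability 0.087, 0.750 and 0.990 at true rates of 10%, 20% and 30%.

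**The case against.** The strongest reply is that oversight exists and a formal boundary is a matter of preference. Plasma is given at a fixed dose under ordinary transfusion requirements. Infusions are followed by haemovigilance, serious events go to the ethics committee, and the authorities can end the study. Donor selection against transfusion-related lung injury, exclusion of recipients with past transfusion allergy, and pathogen inactivation all lower risk. That stands, and it would be wrong to infer that the trial runs without safety oversight. It does not close the gap, because none of these provisions contains a rate or obliges a pause.

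A second reply is that grade III or higher events are common in severe COVID-19, so a limit on the plasma branch alone could fire on background illness. This is fair. Counting only events suspected to be related to plasma, a category section 4.2.9.1 already defines, and showing the control-arm rate alongside reduces the problem. Open-label attribution remains imperfect.

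A third reply concerns the withdrawal list. A reader might infer that patients without both infusions are deleted from the safety rate. The documents do not support that. The same list includes completion of the study and death, so removal most naturally means the end of participation, and section 4.2.9.1 still requires related events to be recorded. What stands is only that the denominator is undefined.

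A reader might also infer that some known share of severe reactions would escape serious-event reporting. The documents give no such share. Section 4.2.9.1 counts prolonged hospitalisation and important medical events as serious, so many could be reported.

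**Conclusion.** The point holds as a gap in the plan. No trial-level action is linked to the grade III or higher rate among plasma recipients, their number has no stated maximum, and the rate's denominator is not defined. This rests on the text available for review.

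The size of any harm cannot be derived from the documents. The probabilities above describe one example rule under an assumed limit, cap and cutoff. They do not measure harm under the current plan, and they depend on how many are treated: at a true rate of 10%, 0.53 with 60 patients and 0.36 with 30. The firm statement is narrower: under the current text, no observed rate obliges a pause. Because real safeguards exist, this is a change that should be made rather than a fatal flaw.

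**What to change.** Add a paragraph to section 4.2.9:

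1. The clinicians set a tolerable rate of grade III or higher events suspected to be related to plasma, and a block size, for example every 10 plasma patients, at which the cumulative count is checked against a table fixed in advance.
2. The denominator is every patient who started a first infusion, taken from the accounting form and including those later removed under section 4.2.3. Events known at a check count at once; later events up to 30 days after the last dose are added when reported.
3. Centres promptly notify the sponsor's adverse event contact of every such event, serious or not, on the Annex V form, which already has fields for grade, study treatment as a possible cause, and notification date.
4. Crossing the limit pauses new plasma assignments, through the existing Annex IX assignment step, until the Research Ethics Committee has reviewed. The control-arm rate of grade III or higher events is shown alongside as background.

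The boundary in the working is one option. The limit, the check and the required action are the essential parts.

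The cost is one paragraph, one table, a short notification step for centres and a review duty for the existing ethics committee. The main downside is an unnecessary pause: in the example, about 9% per 60 patients if the true rate equals the 5% limit and 0.4% if it is 2%.
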